6.12.6. Quick Inventory of Depressive Symptomatology–Self Report 16 items (QIDS-SR16)

The QIDS-SR16 is a self-administered 16-item instrument intended to assess the existence and severity of symptoms of depression as listed in the American Psychiatric Association’s (APA’s) *Diagnostic and Statistical Manual of Mental Disorders, 4th Edition (DSM-IV)* (APA 1994). The QIDS-SR16 scale is used to assess the potential impact of treatment on new onset or changes in depression, thoughts of death, and/or suicidal ideation severity. A patient is asked to consider each statement as it relates to the way they have felt for the past 7 days. There is a 4-point scale

for each item ranging from 0 to 3. The 16 items corresponding to 9 depression domains are summed to give a single score ranging from 0 to 27, with higher scores denoting greater symptom severity. Additional information and the QIDS-SR16 questions may be found at the University of Pittsburgh IDS/QIDS resource page (<http://www.ids-qids.org/>).

The 9 domains assessed by the instrument are defined as:

- 1) **Sleep disturbance** (initial, middle, and late insomnia or hypersomnia): the highest score recorded for the 4 sleep items: #1 (falling asleep), #2 (sleep during the night), #3 (waking up too early) and #4 (sleeping too much). Domain is missing if all items are missing.
- 2) **Sad mood**: Item #5 (feeling sad). Domain is missing if the item is missing.
- 3) **Decrease/increase in appetite/weight**: the highest score recorded for the appetite/weight items: #6 (decreased appetite), #7 (increased appetite), #8 (decreased weight within the last 2 weeks), and #9 (increased weight within the last 2 weeks). Domain is missing if all items are missing or not applicable.
- 4) **Concentration**: Item #10 (concentration / decision making). Domain is missing if the item is missing.
- 5) **Self-criticism**: Item #11 (view of myself). Domain is missing if the item is missing.
- 6) **Suicidal ideation**: Item #12 (thoughts of death or suicide). Domain is missing if the item is missing.
- 7) **Interest**: Item #13 (general interest). Domain is missing if the item is missing.
- 8) **Energy/fatigue**: Item #14 (energy level). Domain is missing if the item is missing.
- 9) **Psychomotor agitation/retardation**: the highest score recorded for the 2 psychomotor items: #15 (feeling slowed down) and #16 (feeling restless). Domain is missing if all items are missing.

The QIDS-SR16 total score is the sum of the above domain scores. The total score will be missing if any domain score is missing. The QIDS-SR16 total scores are categorized as: None (no depression) (0 – 5), Mild (6 – 10), Moderate (11 – 15), Severe (16 – 20) and Very severe (21 – 27).

For both Period 2 and 3 QIDS-SR16 analyses, baseline is defined as the last non-missing assessment recorded on or prior to the date of first injection of study treatment at Week 0 (Visit 2), as for QoL measures. In most cases, this will be the measure recorded at Week 0 (Visit 2).

Summaries will be done by treatment groups for Safety Population in Period 2 and Maintenance Dosing Period Primary Population in Period 3, respectively.

The following summaries will be produced for QIDS-SR16 total score category:

- The number and percentage of patients falling into each QIDS-SR16 total score category at each scheduled visit.
- Shift from maximum baseline to each postbaseline visit in QIDS-SR16 total score category.
- The number and percentage of patients falling into the following categories based upon the maximum postbaseline QIDS-SR16 total score:
 - Improved; maximum postbaseline category < maximum baseline category.

- Worsened; maximum postbaseline category > maximum baseline category.
- Same; maximum postbaseline category = maximum baseline category.

In addition, the number and percentage of patients falling into the following groups based upon the maximum postbaseline QIDS-SR16 item 12 (Thoughts of Death or Suicide) score will be summarized:

- Improved; maximum postbaseline item 12 score < maximum baseline item 12 score.
- Worsened; maximum postbaseline item 12 score > maximum baseline item 12 score.
- Same; maximum postbaseline item 12 score = maximum baseline item 12 score.

6.12.7. Columbia-Suicide Severity Rating Scale (C-SSRS)

The C-SSRS is an assessment tool that evaluates suicidal ideation and behavior. Information on the C-SSRS scale can be found through the following link: <http://www.cssrs.columbia.edu>.

Specifically, the following outcomes are C-SSRS categories and have binary responses (yes/no). The categories have been re-ordered from the actual scale to facilitate the definitions of the composite and comparative endpoints, and to enable clarity in the presentation of the results.

Category 1 – Wish to be Dead

Category 2 – Non-specific Active Suicidal Thoughts

Category 3 – Active Suicidal Ideation with Any Methods (Not Plan) without Intent to Act

Category 4 – Active Suicidal Ideation with Some Intent to Act, without Specific Plan

Category 5 – Active Suicidal Ideation with Specific Plan and Intent

Category 6 – Preparatory Acts or Behavior

Category 7 – Aborted Attempt

Category 8 – Interrupted Attempt

Category 9 – Actual Attempt (non-fatal)

Category 10 – Completed Suicide.

Self-injurious behavior without suicidal intent is also a C-SSRS outcome (although not suicide-related) and has a binary response (yes/no).

Composite endpoints based on the above categories are defined below.

- **Suicidal ideation:** A “yes” answer at any time during treatment to any 1 of the 5 suicidal ideation questions (Categories 1-5) on the C-SSRS.
- **Suicidal behavior:** A “yes” answer at any time during treatment to any 1 of the 5 suicidal behavior questions (Categories 6-10) on the C-SSRS.
- **Suicidal ideation or behavior:** A “yes” answer at any time during treatment to any 1 of the ten suicidal ideation and behavior questions (Categories 1-10) on the C-SSRS.

Given that few or no suicidal ideation or behaviors are anticipated, C-SSRS will be listed by patient and visit. Only patients that show suicidal ideation/behavior or self-injurious behavior without suicidal intent will be reviewed (that is, if a patient’s answers are all ‘no’ for the C-SSRS, then that patient will not be displayed). However, if a patient reported any suicidal ideation/behavior or self-injurious behavior without suicidal intent at any time point, then all

their ideation and behavior will be reviewed, even if not positive. Note, missing data should not be imputed.

The Self-Harm Supplement Form is a 1-question form that is completed, at any visit, including baseline visit, that asks for the number of suicidal behaviors, possible suicidal behaviors, or nonsuicidal self-injurious behaviors the patient has experienced since the last assessment. For each unique event identified, a questionnaire (Self-Harm Follow-up Form) which collects supplemental information on the self-injurious behavior is to be completed. The Self-Harm data will be listed by patient and visit if number of events on Self-Harm Supplement Form is not zero in the CRF '*Self Harm Questionnaire Supplement.*'

6.13. Immunogenicity

6.13.1. Definitions and Terms

The following sample- and patient-related definitions and parameters will be used to describe the immunogenicity data.

6.13.1.1. Sample Category Definitions

Samples are classified into the following categories:

- **Unevaluable sample:** Sample could not be tested for ADA due to sample loss, mishandling, or errors in collection, processing, storage, etc.
- **Anti-drug antibody (ADA) Positive sample:** The presences of ADA is detected and confirmed. The samples are reported as positive. If the sample is positive, a titer value is reported.
- **Neutralizing antibody (NAb) Positive sample:** NAb are reported as detected.
- **ADA Negative sample:** The presence of ADA is not detected and the assay drug tolerance level is not exceeded.
- **NAb Negative sample:** The presence of NAb is not detected and the assay drug tolerance level is not exceeded.
- **ADA/NAb Inconclusive sample:** when ADA/NAb is not detected in a sample but drug is present in the same sample at a level that can cause interference in the ADA/NAb detection method, the negative ADA/NAb result cannot be confirmed and the sample should be considered inconclusive.
 - Confirmation of a negative ADA result was based on ixekizumab concentrations.

6.13.1.2. Patient Category Definitions

The following categories are applied to patients based on the classification of their samples:

- **Unevaluable patient:** a) a patient with no evaluable baseline sample and/or no evaluable postbaseline samples; b) a patient with an evaluable baseline sample but no evaluable postbaseline sample; c) a patient with no evaluable baseline sample, but whose evaluable postbaseline values are all ADA positive or a mix of positive and negative. (Note: If all postbaseline samples are negative, the patient is considered 'evaluable' and will be classified as ADA-negative.)

- **Evaluable patient:** a) Patient with an evaluable baseline sample and at least 1 evaluable postbaseline sample (that is, sample after administration of study drug); b) patient with no evaluable baseline sample whose evaluable postbaseline samples are all ADA negative.

6.13.1.3. Definitions for Clinical Interpretation of Assay Results

- **Baseline:** For immunogenicity analyses during Period 2, baseline is the last nonmissing observation on, or prior to, the date of the first injection of study treatment (Week 0). Unless otherwise specified, the baseline for subsequent treatment periods is defined as the last nonmissing observation on, or prior to, the date of first injection of ixekizumab. For patients originally randomized to ixekizumab during Period 2, baseline is the last non-missing observation on, or prior to, the date of the first injection of study treatment for Period 2 (Week 0). For patients who are originally randomized to placebo in Period 2, baseline is the last non-missing observation on, or prior to, the date of the first injection of ixekizumab. See [Table RHBH. 6.10.](#) for further details.

Table RHBH. 6.10. Definition of Baseline for Immunogenicity Analysis for Maintenance Dosing Period

Period 2 (Induction Period) Randomized Treatment	Week 12 Responder?	Period 3 (Maintenance Dosing Period) Treatment	Relapse (sPGA ≥3)?	Baseline ¹
Ixekizumab	Yes/No	Ixekizumab	Yes/No	Week 0
	Yes	Placebo	Yes/No	Week 0
Placebo	No	Ixekizumab	Yes/No	Week 12
	Yes	Placebo	Yes	Week of Relapse in Period 3
			No	Week 0

Abbreviations: NA = not applicable; sPGA= static Physician Global Assessment.

¹ last nonmissing observation on, or prior to, the date of the first injection of study treatment at the defined Week

- **Baseline ADA positive (preexisting antibody) patient:** ADA detected in a sample collected at baseline.
- **TE-ADA positive patient:** a) a patient with a ≥4-fold (or 2 dilutions) increase over a positive baseline antibody titer; or b) for a negative baseline titer, a patient with an increase from the baseline to a level of ≥1:10.
- **Baseline ADA-negative patient:** ADA is not detected in a sample collected at baseline.
- **TE-ADA inconclusive patient:** A patient without a TE-ADA positive sample and with at least 1 sample for which drug levels may interfere with the ADA assay.
- **TE-ADA negative patient:** A patient who is evaluable for TE-ADA and is not either TE-ADA positive or TE-ADA inconclusive.
- **Incidence of TE-ADA:** Patients with TE-ADA as a proportion of the evaluable patient population during the treatment period. This excludes unevaluable patients.

All ADA positive samples will be evaluated for NAb. Definitions for NAb patient status will be defined as follows:

- **NAb-positive patient:** A patient where a NAb positive result is detected for ≥1 TE-ADA positive samples.

- **NAb-inconclusive patient:** A patient without a NAb positive sample and with at least 1 sample for which drug levels may interfere with the NAb assay.
- **NAb-negative patient:** A patient who is evaluable for NAb and is not either NAb positive sample or NAb inconclusive.

Please see the LY2439821 PSAP v8 section 5.6.4.1.3 (or most current version) for details on the definitions for clinical interpretation of assay results.

6.13.2. Immunogenicity Analyses

Immunogenicity evaluable patients will be identified as TE-ADA positive, TE-ADA negative, or TE-ADA inconclusive, according to the definitions provided in Section 6.13.1.3 and further grouped into TE-ADA status groups and time-varying TE-ADA status groups.

TE-ADA Status Groups:

- TE-ADA status (positive, negative, or inconclusive);
- NAb status (positive, negative, or inconclusive) for TE-ADA positive patients; and
- TE-ADA titer groups for TE-ADA positive patients:
 - Low Titer: TE-ADA titer value (LOCF) <1:160;
 - Moderate Titer: TE-ADA titer value (LOCF) ≥1:160 and <1:1280; and
 - High Titer: TE-ADA titer value (LOCF) ≥1:1280.

Time-Varying TE-ADA Status Groups:

Individual ADA samples will be ascribed into 3 different dichotomous variables as explained in Table RHBH. 6.11. Each variable has possible values of a “greater-TE-ADA status” or a “lesser-TE-ADA status,” in the sense that the level of TE-ADA detected in the greater-TE-ADA category is higher than in the lesser-TE-ADA category.

Table RHBH. 6.11. TE-ADA Status Dichotomous Variables for AE Analysis

TE-ADA Status Dichotomous Variable	Greater-TE-ADA Status	Lesser-TE-ADA Status
TE-ADA positive	TE-ADA positive	not TE-ADA positive
TE-ADA moderate-to-high	TE-ADA positive with moderate titer or high titer	not TE-ADA positive, or TE-ADA positive with low titer
TE-ADA high status	TE-ADA positive with high titer	not TE-ADA positive, or TE-ADA positive with low or moderate titer

Abbreviations: AE = adverse event; TE-ADA = treatment-emergent anti-drug antibody.

Notes: For the purpose of this analysis, TE-ADA Inconclusive is taken to be “not TE-ADA positive.”

A TE-ADA low is defined as a TE-ADA positive with a titer value <1:160; a TE-ADA moderate is defined as a TE-ADA positive with a titer value ≥1:160 and <1:1280; and a TE-ADA high is defined as a TE-ADA positive with a titer value ≥1:1280.

For each TE-ADA status dichotomous variable, a time-varying TE-ADA status will be computed. At time *t*, the TE-ADA status is taken to be the highest of the TE-ADA values bracketing time *t*. More formally, the TE-ADA status at time *t* is given by the greater of (a) the TE-ADA status at the most-recent post-baseline measurement prior to *t*, and (b) the TE-ADA

status at the first TE-ADA post-baseline measurement at or after time t . In this computation, “greater” is given by the greater-TE-ADA status of [Table RHBH. 6.11](#). If there is no value satisfying criterion (a), then the value (b) is used. Similarly, if there is no value (b), then the value (a) is used.

For each TE-ADA status dichotomous variable, patients will be categorized according to whether they were (i) always in lesser-TE-ADA status post-baseline or (ii) at some point post-baseline were in greater-TE-ADA status.

6.13.2.1. Analyses of Characteristics of ADA Immune Response

The analyses of ADA effects will be conducted on all evaluable patients within the defined safety population for Induction Dosing Period (Period 2), and Combined Induction and Maintenance Dosing Periods (Combined Periods 2 and 3, information prior to relapse), and for Maintenance Dosing Period Relapse Population in Maintenance Dosing Period.

Baseline definition for immunogenicity analyses for the Combined Treatment Period is the same as [Table RHBH. 6.10](#).

The overall frequency and percentage (incidence) of patients will be summarized for the TE-ADA status groups and the time-varying TE-ADA status groups. Scheduled visits, unscheduled visits, and repeat measurements will be included.

In addition, the overall frequency and percentage (incidence) of patients will be summarized for the patients who are baseline ADA positive by TE-ADA status groups. For those patients who are TE-ADA positive, a summary of titer values and the proportion of patients who are NAb positive will also be provided.

The time to development of TE-ADAs (TE-ADA positive, Low titer, Moderate titer, High titer, and NAb positive) will be calculated as follows:

$$\text{Time to development of TE-ADA/NAb (in weeks)} = (\text{Date of development of TE-ADA/NAb} - \text{Date of first injection of study treatment} + 1) / 7$$

If a patient has not developed TE-ADA/NAb, they will be censored at the date of the last immunogenicity assessment.

A Kaplan-Meier plot of the time to development of TE-ADA/NAb will be presented by treatment group, if sufficient data is present. The log-rank test will be used to test the null hypothesis against the alternate hypothesis that the time to TE-ADA/NAb is not equal between each ixekizumab dose and placebo. Caution should be exercised in the interpretation of time-to-event analyses and related statistics given the limited sampling scheme for immunogenicity testing.

For each TE-ADA status dichotomous variable (as defined in [Table RHBH. 6.11](#).), summaries will be provided of the total post-baseline time in the greater-TE-ADA status for patients who were at some point post-baseline in the greater-TE-ADA status group. Post-baseline time in greater-TE-ADA status for each patient will be aggregated.

A by-patient listing to include treatment, visit date, visit, ADA result, TE-ADA result, NAb result, ADA titer value, ixekizumab concentration, and ADA and NAb inconclusive results will also be provided.

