- Patients receiving 80 mg ixekizumab Q4W, who relapse, will continue on 80 mg ixekizumab Q4W in order to maintain the study blind and to evaluate the long term efficacy of ixekizumab treatment.
- Patients receiving placebo who relapse will be switched to 80 mg ixekizumab Q4W.

Continued treatment for patients who relapse is provided to understand the longer-term efficacy of ixekizumab when treating patients who experience relapse and to maintain study blinding. See Section 8.3.1 for discontinuation criteria.

**Treatment Assignment for Non-Responders:** Patients randomized to ixekizumab at Week 0 (Period 2) who are non-responders at Week 12 (Visit 7) will receive treatment with 80 mg ixekizumab Q4W during Period 3.

Patients randomized to placebo at Week 0 (Period 2) who are non-responders at Week 12 (Visit 7) will receive treatment with 80 mg ixekizumab Q4W during Period 3. These patients will receive a starting dose of 160 mg ixekizumab as 2 SC injections at Week 12 (Visit 7).

Continued treatment for non-responders is provided so that partial or slow responders to ixekizumab and non-responders to placebo may remain in the study and receive treatment with ixekizumab while maintaining the study blind. Some patients may be deriving benefit from treatment with ixekizumab but will be slow responders or partial responders thereby not meeting the “responder” criteria at Week 12. A discontinuation criterion for patients who remain at or above their baseline sPGA score at both Week 12 and Week 24 is included (see Section 8.3.1) to ensure that patients who have not shown any benefit from treatment with ixekizumab can be treated with any other psoriasis therapy as determined appropriate by the investigator.

Once a patient has switched to 80 mg Q4W, regardless of original treatment in Period 2, re-randomization in Period 3, or any assessments of response/relapse, the patient will remain on 80 mg Q4W.

Patients who discontinue the study for any reason during Period 3 will stop treatment and continue to the ETV prior to entering the Post-Treatment Follow-Up Period (Period 4; Section 7.1.4).

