5.3. Determination of Sample Size

The total sample size for the study is 420 patients randomized at a 2:2:1 ratio in the blinded Induction Dosing Period to 80 mg Q2W, 80 mg Q4W, and placebo, respectively. In order to account for multiple testing for the 2 ixekizumab groups, a 2-sided Fisher's exact test at the 0.025 level is assumed. Assuming the response rates for both sPGA (0,1) and PASI 75 at Week 12 (Visit 7) are 75% for each ixekizumab treatment group and 5% for the placebo group, 168 patients in 80 mg Q2W or 80 mg Q4W versus 84 patients in placebo group will provide >99% power to test the superiority of each ixekizumab dose regimen to placebo for sPGA (0,1) and for PASI 75. These assumptions are based on the integrated results from the pivotal Phase 3 Studies RHAZ, RHBA, and RHBC.

Assuming 70% of the ixekizumab patients are re-randomized in the Maintenance Dosing Period at Week 12 (Visit 7) at a 2:1 ratio to 80 mg Q4W or placebo, approximately 78 patients will be included in 80 mg Q4W group and 39 patients in placebo group. This sample size will:

- provide >99% power to test the difference in the proportion of patients maintaining sPGA (0, 1) from Week 12 (Visit 7) after re-randomization at start of Maintenance Dosing Period to Week 60 (Visit 19) in the Maintenance Dosing Period Primary population between the ixekizumab dosing interval and placebo within the original treatment group, assuming the proportions of patients maintaining sPGA (0, 1) are 70% for 80 mg Q4W and 10% for placebo within each original treatment group (Visit 19). A 2-sided Fisher's exact test at the 0.025 significance level is assumed.
- provide >99% power to test the difference in the proportion of patients maintaining a PASI 75 from Week 12 (Visit 7) after re-randomization at start of Maintenance Dosing Period to Week 60 (Visit 19) in the Maintenance Dosing Period Primary population

between the ixekizumab dosing interval and placebo within each original treatment group, assuming the proportions of patients maintaining a PASI 75 are 70% for 80 mg Q4W and 10% for placebo within each original treatment group. A 2-sided Fisher's exact test at the 0.025 significance level is assumed.

6. A Priori Statistical Methods

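### In the combined-period antibody analysis, placebo patients who switch to ixekizumab have their time to TE-ADA counted from Week 0, although their baseline is the first ixekizumab injection at Week 12 or later

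*SAP*

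**What the plan says.** SAP 6.13.2.1 runs the antibody analyses on three sets: Period 2, Periods 2 and 3 combined (data before relapse only), and the relapse population. It gives a single time-to-event formula in weeks, whose origin is the "Date of first injection of study treatment". Patients without an event are censored at their last immunogenicity assessment.

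For the combined period the same section takes baseline from Table RHBH.6.10. SAP 6.13.1.3 explains that, for patients originally on placebo, "baseline is the last non-missing observation on, or prior to, the date of the first injection of ixekizumab". The table sets this at Week 12 for placebo non-responders and at the week of relapse for placebo responders who relapse. Patients randomised to ixekizumab, and placebo responders who do not relapse, have a Week 0 baseline.

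Protocol 7.1.3 states that patients randomised to placebo "who are non-responders at Week 12 (Visit 7) will receive treatment with 80 mg ixekizumab Q4W during Period 3". Their first injection of any study treatment was placebo at Week 0 (Protocol Table RHBH.9.1).

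The log-rank alternative in SAP 6.13.2.1 is that "time to TE-ADA/NAb is not equal between each ixekizumab dose and placebo". No period is named for it.

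**The concern.** For placebo patients who switch, the event is defined against one date and timed from another. A TE-ADA is a rise over a baseline taken at the first ixekizumab injection, so none can be recorded before that injection. The weeks from Week 0 to the switch are event-free by construction, yet the formula counts them as time at risk. Antibody onset in these patients would look later than it was.

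The development of anti-ixekizumab antibodies is a stated secondary objective, and time to onset is a planned result. The same section also sums post-baseline time in each antibody status, so it would use two time origins for the same patients.

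**Working it through.** **Inputs.** SAP 5.3: "420 patients randomized at a 2:2:1 ratio in the blinded Induction Dosing Period", hence 420 x 2/5 = 168 per ixekizumab arm and 420 x 1/5 = 84 on placebo. Week 12 response rates "are 75% for each ixekizumab treatment group and 5% for the placebo group". Protocol Attachment 1: scheduled antibody samples at Weeks 0, 2, 4, 12, 24, 36 and 60, with a Week 12 window of 84 ± 4 days. Protocol synopsis: 336 of 420 planned to complete (80%).

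**The plan's own figure.** The SAP gives no figure for time to TE-ADA. The arm sizes used here come from its power statement, "versus 84 patients in placebo group will provide >99% power", for which a two-sided Fisher's "exact test at the 0.025 level is assumed". Exact enumeration for 168 versus 84 at 75% versus 5% gives 0.9999997, which agrees.

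**Clock against baseline, read literally.**

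| Patients | Table RHBH.6.10 baseline | Clock start | Gap |
|---|---|---|---|
| Randomised to ixekizumab | Week 0 | Week 0 | none |
| Placebo, non-responder at Week 12 | Week 12 | Week 0 | about 12 weeks |
| Placebo, responder who relapses | week of relapse | Week 0 | more than 12 weeks |
| Placebo, responder without relapse | Week 0 | Week 0 | none |

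Combined-period data stop at relapse, so the third row matters in the relapse-population analysis.

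**Number affected.** Placebo non-responders: 84 x 0.95 = 79.8, about 80 if nobody is lost before Week 12. With 90% or 80% assumed retained to Week 12: 79.8 x 0.9 = 72 or 79.8 x 0.8 = 64. The 80% is the planned completion rate for the whole study, so 64 is pessimistic. Placebo responders: 84 x 0.05 = 4.2, so about 4 could relapse.

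**Size of the shift for placebo non-responders.** Time = (date - origin + 1)/7 on nominal visit days.

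| First positive sample | Origin Week 0 | Origin Week 12 |
|---|---|---|
| Week 24 | (168 + 1)/7 = 24.14 | (84 + 1)/7 = 12.14 |
| Week 36 | (252 + 1)/7 = 36.14 | (168 + 1)/7 = 24.14 |
| Week 60 | (420 + 1)/7 = 60.14 | (336 + 1)/7 = 48.14 |

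Each time falls by 12 weeks. For 80 patients that is 80 x 12 = 960 patient-weeks (80 x 84/365.25 = 18.4 patient-years). For 64 it is 768 patient-weeks (14.7 patient-years).

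**Log-rank test, only if run on the combined period by Week 0 arm.** An illustrative simulation (1,500 trials per setting) compared 168 ixekizumab patients with 80 switched and 4 unswitched placebo patients; the 4 were left out under the corrected clock. It assumed the same TE-ADA hazard after first ixekizumab in both groups, Weibull shape 1 or 0.5, scheduled samples only, and no dropout, relapse or re-randomised withdrawal. Rejection rates at nominal 5%, with the range over the two shapes:

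| Assumed 48-week TE-ADA incidence | Clock as written | Clock from first ixekizumab |
|---|---|---|
| 5% | 0.05-0.06 | 0.06-0.07 |
| 10% | 0.06-0.09 | 0.06-0.10 |
| 20% | 0.09-0.17 | 0.05-0.12 |
| 40% | 0.27-0.41 | 0.04-0.14 |

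The excess that remains under the corrected clock reflects different sample spacing: a switched patient's first scheduled sample after exposure is at 12 weeks, while the ixekizumab arms are sampled at 2 and 4 weeks.

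**The case against.** The best defence is that study treatment is often period-relative in this SAP. The Table RHBH.6.10 footnote ties the first injection of study treatment to the defined week, and SAP 6.1.3 speaks of the first study-treatment injection at Week 12. On that reading the clock already starts at Week 12. The reading is available but not secure. The footnote defines baseline only, the formula does not refer to it, and SAP 6.13.1.3 uses first study treatment (Week 0) and first ixekizumab as different terms. Two programmers could code it differently.

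A reader might infer that the SAP plans a combined-period log-rank test of ixekizumab against a placebo arm that is 95% exposed. The documents do not establish this. Table RHBH.6.1 lists dose-versus-placebo comparisons for Period 2 only, where clock and test are sound. It defines no combined-period groups, and for Period 3 it shows switched placebo non-responders separately without comparison. The as-assigned rule for the Safety Population leaves the damaging version possible, no more.

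A reader might also infer that results are wrong for about one in five exposed patients (79.8/(336 + 79.8) = 19%). Curves are drawn by treatment group. With as-assigned groups, the curves for the 336 patients randomised to ixekizumab are correctly timed and only the placebo-assigned curve is displaced.

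Other mitigations stand in part. Unscheduled, early-termination and hypersensitivity samples may catch an event before Week 24. The plot is made only if data suffice, a by-patient listing gives visit dates, and the SAP urges caution. That caution concerns sparse sampling, however, and not the time origin.

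**Conclusion.** The mismatch is real in the SAP text as written, and limited in reach. In the combined period, placebo non-responders have times to TE-ADA/NAb, and censoring times, about 12 weeks too long, give or take the visit window. The count of at most about 80 rests on the planned 5% placebo response, full retention to Week 12 and all patients being evaluable. In the relapse population the offset is longer, for about 4 patients at most.

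The Period 2 analysis, the curves of patients randomised to ixekizumab, TE-ADA incidence, and the primary and major secondary tests do not depend on this clock in any way that goes wrong.

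The log-rank point is conditional on a combined-period test by Week 0 arm. Even then, the simulation shows no gain from the corrected clock at 5-10% incidence, and material inflation only at about 20-40%. The documents give no TE-ADA incidence, so that part cannot be sized further.

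**What to change.** In SAP 6.13.2.1, start the clock at the injection that defines each patient's Table RHBH.6.10 baseline. That is the first ixekizumab injection for placebo patients who switch, and the Week 0 injection for patients randomised to ixekizumab and for placebo patients who never switch. This keeps the origin defined for placebo patients who never receive ixekizumab, which a plain first-ixekizumab rule would not.

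State that the log-rank test against placebo applies to Period 2 only. Name the combined-period treatment groups, with placebo-to-ixekizumab patients as a separate group without comparison, as Table RHBH.6.1 already does for Period 3.

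The cost is a few lines of SAP text and one derived date variable, with no new data. The loss is any placebo log-rank comparison after Week 12, which the design can hardly support: about 4 of the 84 placebo patients would be expected to remain on placebo beyond that visit.
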